CASTomize Pilot Study Protocol

Principle investigator: [name]

Co-investigator: [name], [name]

Industrial collaborator: [name], [name], [name]

CASTomize pilot study protocol: a randomized controlled trial comparing CASTomize 4D printed cast versus standard of care fiberglass cast on fracture reduction and patient reported outcomes.

Abstract

Background: For many years, traditional fibreglass casting has been the gold standard of immobilisation for distal radius fractures (DRFs). However, the traditional method of casting has obvious disadvantages such as poor patient comfort, inability to be in contact with water, difficulty observing skin underneath and requiring multiple cast changes in the patients care journey. This study compares the Castomize 4D printed casts versus the conventional fiberglass cast in fracture immobilisation, and various patient reported outcomes.

Methods/design: This study is a randomised control trial comparing Castomize 4D printed cast versus conventional fibreglass casts in isolated conservatively treated distal radius fractures. The primary outcome measure is fracture reduction. Secondary outcome measures include patient reported outcome measures such as the Adult Rated Cast Evaluation Questionnaire (ARCEQ)[1][2], comfort of the cast, quality of life assessed with the EQ-5D-5L questionnaire[3], cost-effectiveness and adverse events occurrence. In total, 30 patients will be included and followed for 6 months.

Trial registration: Pending

Registration number: Pending

Background

Displaced distal radius fractures (DRF) are very common in the adult population and their incidence is still on rising trend due to aging population. This is an issue which is pervasive across all ages, but most common in the elderly. In 2019, 180 million fractures happened worldwide. An average of 5 fracture incidents occurs every second. The current gold standard in fracture immobilisation is via the application of a fibreglass cast. However, the current fibreglass cast has multiple disadvantages. The cast is bulky, has poor ventilation and cannot come into contact with water. This gives patients considerable discomfort, and are unable to bathe and provide hygiene to their injured limb for the duration of the casting. Because the cast is not breathable, skin maceration, itchiness and wounds

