may become an issue. In this light, multiple casts changes become necessary to reduce the risk of soft tissue complications and to provide patient comfort. This increases the wastage of materials for the fibreglass casting as well as increases healthcare burden for the cast changes.

Castomize has created a 4D printed cast with its proprietary materials and designs aimed at overcoming the challenges in the traditional casting methods. Its 4D printed casts are lightweight and breathable, allowing contact with water and hygiene. Its design facilitates visualisation of the skin and soft tissue conditions. It is also remouldable, potentially only requiring one device for the duration of the patients care journey.

The design of the 4D printed cast was done in collaboration with orthopaedic clinicians, prosthetists and senior casting technicians optimised for clinical use. A biomechanical test was performed to evaluate the biomechanical properties of the 4D printed cast in comparison to the conventional fibreglass casts and were found to be less stiff and with a lower load to failure. This was however accessed to be not clinically significant.

Therefore, this study aims to compares the Castomize 4D printed casts versus the conventional fiberglass cast in fracture immobilisation and various patient reported outcomes.

Methods/design

This manuscript is written according to the Consolidated Standards for Reporting Trials (CONSORT statement) and Standard Protocol Items: Recommendations for Interventional Trials (SPIRIT guidelines).

Objectives

The primary aim of the study is to assess non inferiority of the Castomize 4D printed cast versus conventional fibreglass casts in fracture immobilisation and reduction.

The secondary aim of the study is to assess differences in patient reported outcomes measures (ARCEQ, comfort of the cast, EQ-5D-5L, cost-effectiveness and adverse events occurrence) in the Castomize 4D printed cast versus conventional fibreglass casts.

Design, participants, interventions and outcomes

Study design and randomization

A randomised controlled trial will be conducted in a single institution: TTSRH.

Patients will be recruited at the outpatient clinic. Patients who meet the inclusion and exclusion criteria will be recruited and randomised into 2 groups. Randomisation will be carried out via block randomisation via a computer generated randomization sequence.

Group 1: Castomize 4D printed cast (Figure 2)

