Analgesic use		✓	✓	✓	✓	✓
EQ 5D5L		✓***		✓	✓	✓
ARCEQ				✓	✓	✓
MCQ- iMTA				✓	✓	✓

PCQ- iMTA				✓	✓	✓
-----------	--	--	--	---	---	---

*X-rays before and after reduction (obtained from standard of care results if available)

**ROM, grip strength done by study team. ROM, DRUJ and Kapandji will be collected as part of standard of care if available

*** EQ 5D5L status pre-fracture and post-fracture sustainment

Table 2 Baseline characteristics

Baseline characteristics	
Date of emergency room visit	Sex
Affected wrist	Date of Birth
Method of reduction	
	Hand dominance
	Mechanisms of injury
	Smoking Status
	General medical history
	Previous injuries of the affected extremity
	La Fontaine criteria

Outcome

Primary outcome The primary outcome of this study is the occurrence of fracture displacement assessed on PA and lateral radiographs at 1, 2 and 6 weeks. Displacement of the radius is defined by: As compared to the post reduction radiograph at T0, Displacement of : > 15° of dorsal angulation, > 20° of volar angulation, < 15° of radial inclination, > 3mm of radial shortening and > 2mm intraarticular step-off or gap. Measurements will be on standard PA and lateral radiographs of the wrist by trained members of the research team.

Secondary outcomes An overview of measurements is shown in Table 1.

- Comfort of the cast assessed via pictorial representation of pressure marks or areas of discomfort.
- Severity of pain evaluated with the Visual analogue Score (VAS)
- Patient will describe their average wrist symptoms over the past week on a scale of 0-10 using Adult Rated Cast Evaluation Questionnaire (ARCEQ) [6][7].
- Quality of life will be assessed using the 5-level EuroQol (EQ-5D-5L) scoring questionnaire.
- Cost-effectiveness will be measured using the Medical Consumption Questionnaire (iMCQ) and the Production Consumption Questionnaire (iPCQ) [8].
- Physical examination:
 - Range of motion (ROM) of the wrist will be measured with a goniometer. ROM concerns dorsal flexion, volar flexion, radial deviation, ulnar deviation, pronation and supination.
 - Grip strength will be measured with a Jamar hydraulic hand dynamometer. The maximum score for each side over 3 attempts will be used
 - Specific testing of the wrist and hand will be performed namely:
 - distal radioulnar joint (DRUJ) stability tested with the DRUJ ballottement test

- opposition of the thumb using the Kapandji score

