- finger stiffness will be measured with finger-to-palm distance, tested from the tip of the finger to the distal palmar crease when the fingers are in maximal active flexion

ROM and grip strength on the injured side will be compared with the uninjured side.

- Number of conversions to surgical treatment and other (serious) adverse events will be monitored. (Eg: Skin complications)

It is expected that a proportion of patients will fail conservative treatment with displacement of the distal radius fracture at week 1 or week 2 follow up. These patients will continue with surgical fixation of their fractures and no further trial procedures will be required.

Adverse events reporting

All adverse events reported by the patient or observed by the treating physician or researcher will be recorded. Serious adverse events (SAE) will be reported to the Domain Specific Review Board (DSRB), which approved the protocol.

Serious adverse events are defined as:

- Skin related problems requiring surgical intervention (Eg: Ulcer, infection, necrosis)
- Compartment syndrome
 - Cast related injury to the patient resulting in loss of limb or life

Study related serious adverse events are defined as:

- Compartment syndrome

Fig 1 Conventional Fiberglass cast[9]

Fig 2 CASTomize 4D printed cast

Data analysis

General descriptive statistics will be performed on baseline patient and fracture characteristics. Patients will be analysed according to the intention-to-treat principle.

Primary outcome

The primary outcome, fracture re-displacement, will be analysed using a mixed-effects logistic regression. To account for clustering, a random intercept for the hospitals will be used. Fixed effects will be the covariates we adjust for as reported in the literature, namely age, presence of osteoporosis, and fracture characteristics. If new prognostic factors will be identified and reported in the literature, these factors will also be added as covariates.

Secondary outcomes

For secondary outcomes, trends between baseline and follow-up time points (T0-T5) will be assessed using linear mixed models for repeated measures. This accounts for comfort of the cast, recovery of function and grip strength, pain severity (VAS), ARCEQ and EQ-5D-5L scores. The number of conversions to surgical fixation and complications will be determined using Fisher Exact or Chi-square test, depending on the magnitude of results.

Cost-effectiveness analysis

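### The primary model's open-ended covariate set is more than 30 patients can support; use one prespecified binary La Fontaine factor instead, and preferably stratify the randomisation on it

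*Combined protocol and SAP*

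**What the plan says.** The Abstract sets the size: "In total, 30 patients will be included and followed for 6 months". Under Study design and randomization the trial has one site ("A randomised controlled trial will be conducted in a single institution: TTSRH") and two arms ("Patients who meet the inclusion and exclusion criteria will be recruited and randomised into 2 groups"). The method is: "Randomisation will be carried out via block randomisation via a computer generated randomization sequence". No stratification factor, block size, allocation ratio or concealment procedure is given.

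Table 2 lists "La Fontaine criteria" among the baseline characteristics. It does not say how they are scored or whether scoring precedes allocation. Osteoporosis has no entry of its own there.

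Under Data analysis, Primary outcome: "The primary outcome, fracture re-displacement, will be analysed using a mixed-effects logistic regression". The covariates follow: "Fixed effects will be the covariates we adjust for as reported in the literature, namely age, presence of osteoporosis, and fracture characteristics". The fracture characteristics are not named, and the next sentence lets further factors enter if the literature reports them. No displacement rate is stated anywhere.

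**The concern.** The plan regards certain factors as prognostic for displacement and handles them only in the regression. That works only if the regression can be fitted. The outcome is binary, the trial has 30 patients, and the covariate list is both undefined and allowed to grow. When some combination of covariates predicts the outcome perfectly in the sample (separation), at least one coefficient has no finite estimate. The analyst must then drop terms or change method after seeing the data. In a trial whose primary aim is non-inferiority on displacement, that leaves the main estimate open to choice.

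Allocation offers no second line of defence, because no prognostic factor is balanced by design even though a candidate is already on the baseline form.

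**Working it through.** **Inputs.** From the documents: 30 patients, two arms, one institution, the covariate list. Assumed, because the documents are silent: 1:1 allocation (15 per arm); La Fontaine criteria dichotomised to mark unstable fractures; 30-50% unstable; 10-20% displacement risk in stable fractures; instability adding 20-40 points; three binary fracture characteristics. With one site the hospital random intercept has nothing to vary over, so an ordinary logistic model is used. The plan gives no figure on this point to reproduce.

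**1. Expected events.** With 40% unstable there are 12 unstable and 18 stable fractures.
- Low end: 18 × 0.10 + 12 × 0.30 = 1.8 + 3.6 = 5.4.
- High end: 18 × 0.20 + 12 × 0.60 = 3.6 + 7.2 = 10.8.

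**2. Events per coefficient.**
- Wide model (treatment, age, osteoporosis, three fracture characteristics; six coefficients): 5.4/6 = 0.9 to 10.8/6 = 1.8.
- Treatment plus one binary factor: 5.4/2 = 2.7 to 10.8/2 = 5.4.

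**3. How often no finite estimate exists.** Trials were simulated with no treatment effect and blocks of 4, 600 per scenario, over the rates in step 1. The wide model showed complete or quasi-complete separation in 16-48% of trials, and treatment plus one factor in 5-24%. Further runs with assumed rates giving the same 5-11 events widened these to about 16-53% and 4-26%, the ranges used here. A hand check shows where the smaller model fails: one route is no event at all among the 18 stable fractures, with probability 0.9^18 = 0.15 at 10% risk and 0.8^18 = 0.02 at 20%.

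**4. Chance imbalance without stratification.** Let K of the 30 fractures be unstable and X of them fall in one arm, X ~ Hypergeometric(30, K, 15). The difference in the share unstable is d = (2X − K)/15, with SD = (2/15) × √[15 × (K/30)(1 − K/30) × 15/29].

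| K | SD of d (points) | P(arms differ by ≥3 patients) | P(≥5) |
|---|---|---|---|
| 9 | 17.0 | 0.427 | 0.109 |
| 12 | 18.2 | 0.264 | 0.060 |
| 15 | 18.6 | 0.466 | 0.143 |

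With K = 12 the difference is always even, so 0.264 is the chance of 4 or more. Multiplied by 20-40 points of added risk, the SD of the shift in the crude risk difference is 17.0 × 0.20 = 3.4 to 18.6 × 0.40 = 7.4 points. At 10 points of added risk it is under 2.

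**5. Scale.** The standard error of a crude risk difference with 15 per arm is √[2p(1 − p)/15]: 14.6 points at p = 0.20 and 17.9 at p = 0.40. The 95% half-widths are 29 and 35 points.

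**6. What stratification adds.** Simulation with 10,000 runs per scenario, blocks of 4, 20% risk in stable fractures and no treatment effect. Standard errors are in points; the last column is Mantel-Haenszel adjustment for the one factor without stratifying.

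| Unstable | Added risk | Unstratified | Stratified | Unstratified, adjusted |
|---|---|---|---|---|
| 30% | 20 | 16.0 | 15.8 | 15.9 |
| 30% | 40 | 17.2 | 16.1 | 16.0 |
| 40% | 20 | 16.4 | 15.8 | 16.3 |
| 40% | 40 | 17.6 | 15.8 | 16.2 |
| 50% | 20 | 16.9 | 16.2 | 16.8 |
| 50% | 40 | 18.0 | 16.6 | 16.7 |

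Including the 30-point scenarios, the SD of the chance shift falls from 3.3-7.5 to 0.6-2.0 points with stratification. The total standard error falls by 0.2 to 1.8 points. Against adjustment alone, the rows above differ by −0.1 to 0.6 points; Monte Carlo error on each entry is about 16/√20,000 = 0.11.

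**The case against.** A reader might infer that unstratified randomisation lets imbalance in instability move the primary result by 4-13 points (3/15 × 20 = 4 up to 5/15 × 40 = 13.3). The documents do not support that reading. Those shifts apply to a crude risk difference, while the planned primary estimate comes from a logistic model that adjusts for fracture characteristics. Chance imbalance under valid randomisation is not bias; it is already part of a standard error of 15-18 points. The added risk behind the shifts is assumed, and an imbalance of 5 or more patients has probability of only 0.06 to 0.14.

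It can also be said that stratifying a 30-patient pilot is optional, that adjusting for the same factor achieves nearly as much, and that small blocks with visibly different casts make the next allocation easier to guess. All of this stands. The documents also never call the La Fontaine criteria an instability measure or place them among the fracture characteristics, so choosing them as the one factor is a judgement for the sponsor to confirm.

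The objection does not rescue the covariate set. The adjustment that performs well in step 6 uses one binary factor. The plan's own adjustment is wider, undefined and open to additions, and that is what 30 patients cannot support.

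**Conclusion.** The point holds as a defect of the primary model. Under assumed rates giving 5-11 displacements, the wide model has no finite estimate in roughly 16-53% of trials, against about 4-26% with treatment plus one binary factor. Both ranges depend on the assumed event rates, and the first also on taking three fracture characteristics; more covariates or fewer events would make it worse.

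The absence of stratification is secondary. Stratifying steadies the comparison visibly (SD of the chance shift from about 3-7.5 to about 1-2 points) but lowers the total standard error only from about 16-18 to 16-17 points. It is a cheap improvement and not a correction of bias. The whole point matters less than the missing non-inferiority margin and the missing basis for the sample size.

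**What to change.** In Data analysis, Primary outcome, replace the covariate list and the provision for adding newly reported factors with treatment plus one binary covariate: La Fontaine criteria met, fewer or more, with the cut-point fixed before the first patient. Since even this model can fail, name in advance the method to be used when no finite estimate exists, for example Firth's penalised likelihood.

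Preferably, under Study design and randomization, stratify the block randomisation on the same factor. Score it before allocation, and use varying block sizes that are concealed from those who enrol.

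Costs: a second randomisation list, and one field that must be completed before allocation. Small blocks are more predictable in an open-label single-centre trial, which varying and concealing the sizes reduces but does not remove. With blocks of 4 in two strata the arm totals would differ by 0 or 2. The primary analysis would no longer adjust for age and osteoporosis; these can be described by arm in the baseline table. The covariate change needs only to precede sight of outcome data, provided the cut-point is already fixed; stratification is possible only before enrolment.

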Patients randomized to group 1 will undergo fracture immobilisation with the Castomize 4D printed cast via the care team (Casting technician/ clinical team). The Castomize 4D printed cast is appropriately heated and then moulded to the patients wrist as per usual manipulation and reduction techniques. The cast is held in position until hardened.

Group 2: Conventional casting (Figure 1)

Patients randomized to group 2 undergo fibreglass casting as per the standard of care.

In both groups, post casting X-rays are taken to assure fracture reduction and recasting may be attempted in the event of inadequate fracture reduction.

A patient information sheet will be provided to the patient explaining the study protocol, and what to look out for in caring for their casts.

Inclusion criteria

- Age \geq 21 years
- Distal radius fracture for conservative treatment within 3 weeks of initial injury

Exclusion criteria

- Concomitant injuries to the ipsilateral extremity, interfering with the treatment of the DRF (Example: concomitant elbow fracture that requires further immobilisation with a above elbow cast)
- Inability to complete study forms due to any cognitive, mental issues.
- Pregnant women

Study procedures and timeline

Measurements will take place at 6 time points as shown in Table 1. These time points are baseline (T0), 1 week (T1), 2 weeks (T2), 6 weeks (T3), 3 months (T4) and 6 months (T5) after inclusion in the study. At T0, baseline characteristics will be gathered. An inclusion form will be filled in by the treating physician providing fracture and treatment-specific information. Second, patients receive a questionnaire, providing predominantly patient and injury-specific information. The list of baseline characteristics is shown in Table 2. Patients receive questionnaires at T1 to T5. These questionnaires are carried out by phone call. Posterior-anterior (PA) and lateral radiographs of the wrist will be taken at T0 (before and after reduction) and during follow-up at T1 –T4 as per standard of care. Physical examination of the wrist will take place at T4 and will be performed by the research team. Study visit may be administered via phone call. Functional tests will be performed at patient earliest appointment.

Table 1 Schedule of activities

	T0 Baseline	T1 D7 \pm 3	T2 D14 \pm 3	T3 D35 \pm 7	T4 D84 \pm 14	T5 D168 \pm 21
Inclusion form	✓					
X-rays*	✓	✓	✓	✓	✓	
Functional tests**					✓	✓
VAS		✓	✓	✓	✓	✓
Photograph		✓				
Comfort of cast		✓	✓	✓		

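### Entry does not require a reduction, but the primary endpoint is measured from a post-reduction film that some eligible patients lack and that for others may predate randomisation

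*Combined protocol and SAP*

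**What the plan says.** **Who enters.** Under Inclusion criteria the only fracture requirement is "Distal radius fracture for conservative treatment within 3 weeks of initial injury". There are three exclusions: one begins "Concomitant injuries to the ipsilateral extremity, interfering with the treatment of the DRF", and the others concern inability to complete the forms and pregnancy. None removes undisplaced or unreduced fractures. The Abstract is equally broad: "isolated conservatively treated distal radius fractures".

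**What is measured.** Under Outcome, displacement at 1, 2 and 6 weeks is judged "As compared to the post reduction radiograph at T0". Under Data analysis: "The primary outcome, fracture re-displacement, will be analysed using a mixed-effects logistic regression".

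**What implies a reduction.** The Background begins "Displaced distal radius fractures (DRF) are very common in the adult population". Study procedures and timeline schedules T0 radiographs before and after reduction, and Table 2 records the method of reduction. The first footnote to Table 1 says the reduction films come from routine care where they exist. Study design and randomization plans an X-ray after casting in both groups and allows recasting if the reduction is inadequate.

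**Allocation and aim.** Recruitment is at the outpatient clinic. "Randomisation will be carried out via block randomisation via a computer generated randomization sequence"; no stratification is stated. The primary aim is to "assess non inferiority of the Castomize 4D printed cast versus conventional fibreglass casts in fracture immobilisation and reduction". The model adjusts for age, osteoporosis and fracture characteristics that are not listed.

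**The concern.** The entry criterion and the endpoint describe different patients. The endpoint assumes that every patient has been reduced and has a film recording that reduction at T0. The criterion guarantees neither.

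Two consequences concern the validity of the endpoint. An unreduced fracture has no film of the named kind, so whoever reads the radiographs must improvise a reference or leave the outcome missing. A fracture reduced earlier (Table 2 records an emergency room visit, and entry is allowed up to 3 weeks after injury) may have its only post-reduction film from before allocation. Position lost between that film and application of the allocated cast would then be scored as failure of that cast.

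A third consequence is conditional. If unreduced fractures displace less often, they add mostly non-events to both arms and bring the crude risk difference closer to zero. This matters for non-inferiority, because the Background reports that the new cast was less stiff and failed at a lower load in bench testing, although this was judged not clinically significant.

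**Working it through.** **Step 1. Reference film by type of eligible patient.**

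| Patient | Post-reduction film | Is the reference defined? |
|---|---|---|
| Reduced at T0 in the allocated cast, no recasting | Yes, in the allocated cast | Yes |
| Reduced before recruitment | Yes, possibly before allocation | No: the plan does not choose between that film and the post-casting film |
| Not reduced | None | No: a post-casting film is planned but not named as the reference |
| Recast at T0 | More than one post-casting film | No: the plan does not say which counts |

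The endpoint is fully specified for the first row only. The documents do not say how many patients fall in each row.

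**Step 2. Is there a plan figure to reproduce?** No. The total of 30 is given without alpha, power, margin or event rate.

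**Step 3. Effect of unreduced fractures on the crude comparison.** All rates here are assumptions. Let f be the unreduced share. Then

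p(arm) = (1 − f) × p(reduced) + f × p(unreduced).

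Assume that reduced fractures displace in 30% with fibreglass and 50% with the new cast (difference 20 points, odds ratio 2.33). Worked case with f = 0.4 and unreduced risk 5% in both arms:
- fibreglass 0.6 × 0.30 + 0.4 × 0.05 = 0.20
- new cast 0.6 × 0.50 + 0.4 × 0.05 = 0.32
- difference 12 points; odds ratio (0.32/0.68)/(0.20/0.80) = 1.88

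| Unreduced share | 0% | 20% | 40% | 60% |
|---|---|---|---|---|
| Difference in points, unreduced 5% in both arms | 20.0 | 16.0 | 12.0 | 8.0 |
| Crude odds ratio, same case | 2.33 | 2.08 | 1.88 | 1.69 |
| Expected events among 30, same case | 12.0 | 9.9 | 7.8 | 5.7 |
| Difference in points, same odds ratio in unreduced (5% v 10.9%) | 20.0 | 17.2 | 14.4 | 11.6 |
| Crude odds ratio, same case | 2.33 | 2.19 | 2.10 | 2.05 |

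The crude risk difference and odds ratio shrink in both cases. The crude risk ratio need not: in the second case it moves from 1.67 to 1.77 at 60% unreduced. The plan does not state the effect scale.

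**Step 4. What this could do to a conclusion.** The following are further assumptions: a 20-point margin, 15 per arm, and non-inferiority declared when the upper limit of a 95% Agresti-Caffo interval is below the margin. Reduced fractures then lie exactly on the margin. By exact binomial enumeration, with 5% unreduced risk in both arms, the chance of declaring non-inferiority is 2.3%, 4.2%, 7.5% and 12.9% at 0%, 20%, 40% and 60% unreduced. With the same odds ratio in unreduced fractures it is 2.3%, 3.6%, 5.6% and 8.3%.

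**Step 5. Chance imbalance in reduction status.** Assume 15 per arm. With K reduced among 30, the number x in one arm is hypergeometric: P(x) = C(K, x) × C(30 − K, 15 − x) / C(30, 15). For K = 15, the arms differ by 5 or more when x ≤ 5 or x ≥ 10, with probability 0.143. For K = 10, they differ by 4 or more when x ≤ 3 or x ≥ 7, with probability 0.245; K = 20 gives the same. This has no direction and bears on precision only.

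**The case against.** - **A broad population is legitimate.** The Abstract and the inclusion criterion agree with each other, and the aim covers immobilisation as well as reduction. A smaller difference in a mixed population is the true difference in that population. This stands: it would be wrong to say that the rest of the protocol consistently describes displaced, reduced fractures, or that eligibility must be narrowed.
- **A usable film is already planned.** Both groups have an X-ray after casting, so unreduced patients could have an in-cast reference and earlier slippage need not be charged to the cast. This stands in part. The film is planned, but the endpoint does not name it, and the Table 1 footnote makes reduction films depend on availability.
- **Some thresholds could be read as absolute positions.** Radial inclination below 15° is an example, and it could be scored on a single film. However, the definition places all the thresholds under the comparison with T0.
- **The model adjusts for fracture characteristics.** If these include reduction status and the odds ratio is constant, the adjusted odds ratio is not biased by the mix; the cost is mainly fewer events and a wider interval. This also stands, but reduction status is not named, the adjustment is fragile with 30 patients, and no covariate supplies a missing reference film.
- **Chance imbalance is ordinary sampling error.** Correct. It justifies stratifying for precision and is not evidence of bias.

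**Conclusion.** The mismatch is established from the text. The primary endpoint cannot be scored as written for eligible unreduced fractures. For fractures reduced before recruitment, it may count displacement that occurred before allocation. Neither conclusion needs an assumed rate, although how many patients are affected is unknown.

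The effect on the crude risk difference is conditional on unreduced fractures having a lower displacement risk. Under the assumed rates, 20 points falls to between 12 and 14.4 points at 40% unreduced; the documents cannot confirm or replace those figures.

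A reader might infer that the trial is biased towards non-inferiority by a known amount. The documents do not support that: they give no reduced share, event rate, margin or effect scale, and the planned model may adjust for reduction status. In practice the missing margin and the small sample weigh more. With 15 per arm, 80% power at one-sided 0.025 needs a margin of about 31 to 50 points at event rates of 10% to 40%. That is a separate point and does not remove this one. The change should be made before enrolment.

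**What to change.** 1. Reconcile the inclusion criterion, the T0 procedures, the Table 1 footnote and the primary outcome, so that all describe the same patients and the same film.
2. For every patient, reduced or not, define the reference as the final accepted PA and lateral film in the allocated cast at T0, after any recasting at T0. This is the post-casting X-ray already planned. The first in-cast film would not do, because the protocol allows recasting and that film may show a position that was not accepted.
3. Stratify the block randomisation by reduced versus not reduced at entry, and name reduction status as a covariate in the primary model.
4. Report the primary comparison in reduced fractures as a prespecified supportive analysis.

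The cost is protocol wording, one extra stratum and one extra covariate in a 30-patient trial. Precision in the reduced subset will be low: if half are reduced, it holds 30 × 0.5 = 15 patients, so that analysis should not carry the conclusion. Restricting entry to displaced, reduced fractures is an option for the sponsor. It would simplify the endpoint but narrow recruitment, and it is not a required correction.

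### The primary outcome definition cannot be applied as written: the radial inclination limit contradicts its own T0 lead-in, and the five limits are joined so that no film can meet them all

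*Combined protocol and SAP*

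**What the plan says.** The only definition of the primary outcome is in the combined protocol and SAP under Outcome, Primary outcome. The outcome is whether displacement occurs on the radiographs at the three follow-up points T1 to T3. The defining sentence opens "As compared to the post reduction radiograph at T0, Displacement of : > 15° of dorsal angulation, > 20° of volar angulation" and closes "< 15° of radial inclination, > 3mm of radial shortening and > 2mm intraarticular step-off or gap". No section says how many limits must be met, and no limit is given a reference of its own.

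Other sections bear on how it would be scored:

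- **Name of the outcome.** The Abstract says "The primary outcome measure is fracture reduction". The Objectives set out "to assess non inferiority of the Castomize 4D printed cast versus conventional fibreglass casts in fracture immobilisation and reduction". The Data analysis section says "The primary outcome, fracture re-displacement, will be analysed using a mixed-effects logistic regression", and the Cost-effectiveness analysis counts re-displacements as its effect measure.
- **T0 film.** Study design and randomization says "post casting X-rays are taken to assure fracture reduction and recasting may be attempted" if the reduction is inadequate. Study procedures and timeline plans T0 films before and after reduction. The Table 1 footnote qualifies this: "X-rays before and after reduction (obtained from standard of care results if available").
- **Consequence of displacement.** The end of the Outcome section expects that "a proportion of patients will fail conservative treatment with displacement of the distal radius fracture" at week 1 or 2, and says that these patients go on to surgical fixation with no further trial procedures.

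**The concern.** This one sentence produces the binary variable for the primary logistic regression, for the non-inferiority aim and for the cost-effectiveness ratio. Followed literally, it gives either no events at all or, if the limits are taken as alternatives, an event for every fracture that stays where it was reduced. Whoever scores the films must therefore depart from the text, and the text does not say in which direction. The measurements are made by members of the research team, and the plan does not mention masking them to allocation. An unwritten choice of reading could thus be made after films and allocations are known. In a trial of 30, a few patients scored differently are a visible part of the comparison.

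**Working it through.** The plan states no event rate, so there is no figure to reproduce. The check applies the printed limits to the printed lead-in. The limits come from Outcome, Primary outcome, and the 30 patients from the Abstract. The example wrists are invented to test the logic.

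**1. Radial inclination under the T0 lead-in.** An unmoved wrist, 22° at T0 and 22° at follow-up, has a change of 0°. Since 0 < 15, the limit is met. A wrist that falls from 22° to 5° has lost 17°. Since 17 is not below 15, the limit is not met. With a signed change (5 − 22 = −17), the moved wrist meets it, but so does the unmoved one, so the limit separates nothing. Read as a value on the film, it behaves sensibly: 22° is no event and 5° is an event. It therefore works only as a value, which contradicts the lead-in.

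**2. The conjunction.** Dorsal and volar angulation are opposite directions of one angle. A single film cannot exceed 15° one way and 20° the other, whether as values or as changes from T0. A grid of tilt −60° to 60°, inclination −10° to 40°, shortening 0 to 10 mm and step-off 0 to 6 mm, in unit steps, has 121 × 51 × 11 × 7 = 475,167 combinations, and none meets all five limits. Pooling films across visits is no practical escape: the wrist would have to swing by more than 15 + 20 = 35° between visits and meet the other three limits as well.

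**3. Frame of the remaining limits, taking any one limit as enough.**

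| Invented wrist, T0 to follow-up | As value on the film | As change from T0 |
|---|---|---|
| 5° dorsal to 16° dorsal | 16 > 15: event | 16 − 5 = 11: no event |
| 10° volar to 8° dorsal | 8: no event | 10 + 8 = 18 > 15: event |
| Step-off 1.0 mm to 2.5 mm | 2.5 > 2: event | 2.5 − 1.0 = 1.5: no event |

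The frames disagree in both directions, so replacing *and* with *or* does not settle the definition. For shortening, change is the natural reading, because T0 is the only radiographic comparator stated.

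**4. Limits already exceeded at T0.** A wrist with 13° of inclination at T0 and 13° at follow-up has not moved, but it is an event on the value reading unless findings already present at T0 are excluded. The term re-displacement suggests exclusion. The Abstract and Objectives, which speak of reduction, leave it open.

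**5. Weight of one patient.** The allocation ratio is not stated. At 1:1, 30/2 = 15 per arm and 1/15 = 6.7 percentage points. At 2:1 (20 and 10), one patient is worth 1/20 = 5.0 or 1/10 = 10.0 points.

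**The case against.** The strongest reply is that a sensible reader would not score the list as a conjunction, and that the lead-in already names T0 as the reference. On this view only one item is badly worded.

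Much of that stands. A reader might infer that the plan gives no reference for the other four limits. It does: on its face the lead-in makes all five changes from T0. Their frame is in doubt only by inference, because the same lead-in cannot hold for inclination, and for shortening there is little doubt.

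A reader might also infer that the reference film is undefined. The plan largely answers this. It schedules a T0 film after reduction and a film after casting in both groups, and in the 4D-printed group the cast is moulded during reduction, so the two may be the same film. What remains is the recast patient and the footnote's availability condition.

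The reply does not remove the two textual faults. The probable intent of any one limit is not written anywhere. It also matters beyond scoring, because the same section links displacement to surgical fixation.

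**Conclusion.** The definition is wrong as written in two respects that need no outside input: the inclination limit contradicts the lead-in, and the literal conjunction makes the event impossible. The frame of the angulation and step-off limits is uncertain rather than shown to be wrong. This should be corrected before any follow-up film is read, since it is the only definition of the primary outcome.

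The size that can be stated is the weight of one patient: 6.7 percentage points of an arm's rate, assuming 1:1 allocation. A reader might go further and conclude that a particular share of patients would be reclassified, or that the non-inferiority result would reverse. The documents do not support either. They give no distribution of fracture movement, no expected event rate and no margin against which a reversal could be judged.

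**What to change.** Keep the stated limits and the planned films. Before any follow-up film is read, restate Outcome, Primary outcome so that it says:

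1. How the limits combine. If one is enough, say so, for example *any one of the following on a T1, T2 or T3 film*.
2. For each of the five limits, whether it is the value on the follow-up film or the change from the T0 film, with radial inclination reworded so that no change does not by itself meet it.
3. Which T0 film is the reference when the cast is redone, how a patient without that film is scored, and whether a limit already exceeded on it counts.

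Run the primary comparison once under the alternative frame as a sensitivity analysis, reported as exploratory. Use one term for the outcome in the Abstract, Objectives, Outcome, Data analysis and Cost-effectiveness sections. Reconcile the scoring definition with the statement that patients displaced at week 1 or 2 go on to surgical fixation. The sponsor chooses the rule. This point concerns endpoint scoring and sets no rule for surgery.

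The cost is a wording change and one extra analysis, with no new films, measurements or patients. With 30 patients, that analysis may differ from the primary result by chance, and the report should say so.
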